### **4.5 Secondary Endpoints – HIV cascade and clinical outcomes**

1. HIV viral load at 6 months post-discharge.
2. Readmission to hospital within 6 months of discharge
3. Mortality within 6 months of discharge.
4. Retention in HIV care after discharge defined by no gap of >28 days off ART from discharge date to 6 months post-discharge date.
5. Engaged in ART care at a community (non-referral site) clinic at 6 months post-discharge
6. Mental health outcomes (i.e. depression level) post intervention

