- **Outpatient follow-up verification:** At the first visit (within one week), the CHW will discuss with patient and care giver the timing and location of follow-up. They will remind the client by phone 1 day before and if the patient misses that visit, the CHW will arrange to

accompany the patient to the clinic at the soonest possible time. In Zambia, the standard post-hospital follow-up at outpatient occurs at 2 weeks.

- **Identify knowledge gaps among patient and family related to the reason for illness:** The CHW will document the reason for illness and the family's and patient's understanding of the illness and list any questions they have.
- **Screening for behavioral health comorbidities:** The CHW will screen for symptoms of depression and unhealthy alcohol use at ~1 month after discharge and make referrals as feasible.
- Conduct a quick home observation to document the patient home environment to assess barriers existing as well as facilitators to engagement.

To ensure that CHWs are fully supported, they will meet with CLO once per week to discuss their clients. CLOs reinforce adherence to the model. The CHW will also call their CLO supervisor urgently from the client household if certain parameters are outside of range, such as elevated pulse. The CLO can then engage the physician as needed.

The ReCharge CHW intervention holds promise. First, it was designed based on a rigorous local formative project (ReCharge 1) and with inputs from clinical, community, and program experts and MOH. Also, CHW support is both highly feasible and acceptable, but can reduce death in PLWH. In the REMSTART trial, weekly home visits plus testing and treatment of cryptococcal disease among people with low CD4 reduced mortality significantly. Many of our clients will have CD4 >200; however, given their recent hospitalization, they are at high risk of mortality.

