At the six-month follow-up, we will re-interview up to 16 of these 24 for a second IDI reflecting on patient experience and capturing their perceptions of whether and how CHW follow-up addressed barriers or enhanced enablers to care to assess feasibility and acceptability. We will work with CLOs, CHWs, and clinic-level data to stratify the endline sample by patient outcome (retained versus not retained), and purposively select patients within strata to capture a range of demographic and facility-level characteristics. The same interviewer who interviewed the patient at time 1 will return to complete the interview at time 2. Again these interviews would take place at a time and place convenient for the patient. The interviewer will then ask the patient for permission to invite their primary caregiver to be interviewed as well. If the patient and the caregiver consent, then the interviewer will also interview the care giver. Caregiver IDIs will address the experience of caring for the discharged patient throughout the intervention and their perceptions of CHW follow-up. When non-retained participant deaths are ascertained, we will try to perform an IDI with the caregiver (after reasonable time elapses for mourning) to understand the barriers to care, co-morbidities and other mortality causes (we estimate up to 4 such cases based on COLAH); we may therefore have more caregiver than patient endline interviews.

In addition to the longitudinal sub-sample of 16 patients stratified by re-engagement in care outcomes; we will also purposively sample up to 8 patients (for a total of up to 24 endline interviews) who showed signs of mental illness or behavioral health concerns (i.e., scored above  $\geq 10$  points on the PHQ-9 screening tool for depression and related concerns; or scored above  $\geq 3$  on the AUDIT-C), and were referred by the team for mental health services. We will interview these patients to understand experiences of patients with mental health related challenges such as depression and alcohol abuse, and to assess how the referral process and related services were received by such patients. These interviews will be essential toward preparing for future work with patients experiencing similar challenges.

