**22. Appendix 9: Patient Health Questionnaire 9 (PHQ-9): Nyanja**

Pa milonga iwiri yapita, kodi ni kangati kamene munavutisidwa ndi yali mavuto aya yokonkapo?			
(Chongani mu kabokosi kuti muonese yankho yanu)			
1	Kukondwera pang'ono kapena kusangalala kung'ono mukuchita zinthu	 0.Kulibe ngankhale pang'ono  1.Masiku angapo  2.Kupambana pa hafu ya masiku  3.Pafupi-fupi masiku onse	
2	Kumvera kuipa, wodidikizidwa mu maganizo, kapena wopanda chiyembekezo	 0.Kulibe ngankhale pang'ono  1.Masiku angapo  2.Kupambana pa hafu ya masiku  3.Pafupi-fupi masiku onse	
3	Kuvutika kugona kapena kusagona, kapena kugona kwambiri	 0.Kulibe ngankhale pang'ono  1.Masiku angapo  2.Kupambana pa hafu ya masiku  3.Pafupi-fupi masiku onse	
4	Kumvera kulema kapena kunkhala ndi mphamvu zing'ono	 0.Kulibe ngankhale pang'ono  1.Masiku angapo  2.Kupambana pa hafu ya masiku  3.Pafupi-fupi masiku onse	
5	Kunkhala ulibe chilakolako chakudya safuna kapena kudya kwambiri	 0.Kulibe ngankhale pang'ono  1.Masiku angapo  2.Kupambana pa hafu ya masiku  3.Pafupi-fupi masiku onse	
6	Kumvera kuipa pa za inu mweka -- kapena kuti munakangiwa kapena munazilekelela kapena kulekelela banja	 0.Kulibe ngankhale pang'ono  1.Masiku angapo  2.Kupambana pa hafu ya masiku  3.Pafupi-fupi masiku onse	
7	Kuvutika kuika maganizo pamodzi pa zinthu, monga kuwerenga nyuzipepa kapena kuonelela TV	 0.Kulibe ngankhale pang'ono  1.Masiku angapo  2.Kupambana pa hafu ya masiku  3.Pafupi-fupi masiku onse	

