**23. Appendix 10: Patient Health Questionnaire 9 (PHQ-9): Bemba**

Pa milungu ibili iyapita bushe miku inga iyo mwacushiwapo namafya ayali fyонse ayakonkelepo aya? (Click the circle to indicate your answer)			
1	Ukutemwa ukunono nangu ukusekelamo mukucita ifintu	 0.Awe nelyo panono  1.Inshiku ishingiko  2.Ukucila pali hafu ya nshiku  3.Mupepi na cila bushiku	
2	Ukushisansamuka, ukutitikishiwa nangu ukushikwata isubilo	 0.Awe nelyo panono  1.Inshiku ishingiko  2.Ukucila pali hafu ya nshiku  3.Mupepi na cila bushiku	
3	Ubwafya bwakulala nangu ukulalisha nangu ukulalisha sana	 0.Awe nelyo panono  1.Inshiku ishingiko  2.Ukucila pali hafu ya nshiku  3.Mupepi na cila bushiku	
4	Ukumfwa uwanaka nangu ukukwata amaka ayanono	 0.Awe nelyo panono  1.Inshiku ishingiko  2.Ukucila pali hafu ya nshiku  3.Mupepi na cila bushiku	
5	Ukushifwaya ukulya nangu ukulya sana	 0.Awe nelyo panono  1.Inshiku ishingiko  2.Ukucila pali hafu ya nshiku  3.Mupepi na cila bushiku	
6	Ukumfwa ububi palwa mwebene mweka – nangu ukuti mwalifilwa nangu mwalilekelesha nangu mwalilekesha ulupwa	 0.Awe nelyo panono  1.Inshiku ishingiko  2.Ukucila pali hafu ya nshiku  3.Mupepi na cila bushiku	
7	Ubwafya bwakubika amaano pa fintu, pamo nga ukubelenga nyunshipepa nangu ukutamba TV	 0.Awe nelyo panono  1.Inshiku ishingiko  2.Ukucila pali hafu ya nshiku  3.Mupepi na cila bushiku	
8	Ukwenda nangu ukulanda panono-panono sana icakuti; Bambi kuti baishiba? Nangu ukupilibula – ukuba uushiteka umutima pansi umutima pansi icakuti mwaleenda-enda sana ukucila lyonse	 0.Awe nelyo panono  1.Inshiku ishingiko  2.Ukucila pali hafu ya nshiku  3.Mupepi na cila bushiku	

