**24. Appendix 11: Patient Health Questionnaire 9 (PHQ-9): English**

In the past two weeks, how many times have you been bothered by these problems? (Click the circle to indicate your answer)			
1	A little interest or pleasure in doing things	 0.Not at all  1.A few days  2.More than half a day  3.Almost everyday	
2	. Feeling down/bad, depressed, or hopeless	 0.Not at all  1.A few days  2.More than half a day  3.Almost everyday	
3	Difficulty falling asleep or staying asleep, or sleeping too much	 0.Not at all  1.A few days  2.More than half a day  3.Almost everyday	
4	Feeling tired/weak or having little energy	 0.Not at all  1.A few days  2.More than half a day  3.Almost everyday	
5	Poor appetite or overeating	 0.Not at all  1.A few days  2.More than half a day  3.Almost everyday	
6	Feeling bad about yourself or that you are a failure or let yourself or your family down	 0.Not at all  1.A few days  2.More than half a day  3.Almost everyday	
7	Difficulty/trouble concentrating on things, such as reading or watching TV	 0.Not at all  1.A few days  2.More than half a day  3.Almost everyday	
8	Moving or speaking very slowly that other people could have noticed or the opposite – being so fidgety or restless that you have been moving around a lot more than usual	 0.Not at all  1.A few days  2.More than half a day  3.Almost everyday	
9	The idea that it would be better to die or to do it yourself in any way	 0.Not at all  1.A few days  2.More than half a day	

		 3.Almost everyday
	Score "Several days"	
	Score "More than half the days"	
	Score "Nearly every day"	
	Enter Total Score:	

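### On all nine scored items of the English PHQ-9, the 2-point answer refers to half a day, while the form's own score row counts days

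*Combined protocol and SAP*

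**What the plan says.** The English PHQ-9 (Appendix 11) asks "In the past two weeks, how many times have you been bothered by these problems" and gives four answers numbered 0 to 3 on each of nine scored items. On all nine, the answer worth 2 is "2.More than half a day". The row of the same form where the 2-point answers are totalled is labelled "Score 'More than half the days". The answer worth 2 is "2.Kupambana pa hafu ya masiku" on the Nyanja form (Appendix 9) and "2.Ukucila pali hafu ya nshiku" on the Bemba form (Appendix 10).

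The score is used in several places:

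- Section 5.3.2 purposively samples up to 8 further endline interviewees, using a cut of 10 "points on the PHQ-9 screening tool for depression and related concerns" as one route in.
- Section 4.5 lists as its sixth secondary endpoint "Mental health outcomes (i.e. depression level) post intervention".
- Exploratory objectives 2 and 5 in Section 4.3 concern the prevalence of behavioral health comorbidities and of depression.

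On timing, Section 5.1 says "The CHW will screen for symptoms of depression and unhealthy alcohol use at ~1 month after discharge and make referrals as feasible", and Section 5.2.4 lists a PHQ among the one-month measures.

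**The concern.** A label that changes the meaning of an answer on every scored item is a measurement error built into the form. A respondent who takes the English wording at face value can truthfully choose the 2-point answer for a symptom felt on a single day. Another, troubled on most days, may find that wording too short and choose a different answer. Either way the total no longer measures what the cut of 10 presupposes, and the three language forms may not yield the same scale. At stake are the selection of the mental-health interviewees, the depression prevalence figures and secondary endpoint 6.

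The same instrument raises two points of missing detail. Endpoint 6 is not dated, and the part of objective 5 that concerns depression during hospitalization has no depression measure listed in hospital.

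**Working it through.** The plan gives no figure of its own on this point, so there is nothing to reproduce. The check sets the forms side by side and then applies simple score arithmetic.

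**1. The forms compared**

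| Form | 2-point answer | Same form's score row |
|---|---|---|
| English (Appendix 11) | "2.More than half a day" | "Score 'More than half the days" |
| Nyanja (Appendix 9) | "2.Kupambana pa hafu ya masiku" | Same words apart from one particle |
| Bemba (Appendix 10) | "2.Ukucila pali hafu ya nshiku" | Printed in English, with the day-count wording |

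The Nyanja 2-point answer uses the same noun as its 1-point and 3-point answers. The Bemba 2-point answer uses the noun of its 1-point answer. Only the English form conflicts with its own score row in meaning. Its 1-point and 3-point labels also differ from their rows (a few against several; almost against nearly), but those are near-synonyms. The wording is the same on nine items while the score row reads correctly, so a fault in reading the PDF is implausible.

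**2. What the printed label means**

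- Window: two weeks = 14 days.
- Intended lower threshold for 2 points: more than 14 / 2 = 7 days.
- Printed lower threshold for 2 points: more than 0.5 day.

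The printed answer has no upper limit, so it contains a few days. The 1-point and 2-point answers overlap.

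**3. What that can do to a score**

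There are nine items scored 0 to 3, so the total runs from 0 to 9 × 3 = 27. Section 5.3.2 prints the cut as above ≥10; I take it as 10 or more.

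- Nine items truly at 1 give 9. One of them ticked as 2 gives 9 + 1 = 10, which reaches the cut.
- Five items truly at 1 give 5. All five ticked as 2 give 5 × 2 = 10, which reaches the cut.
- Four items truly at 1 give 4. All four ticked as 2 give 4 × 2 = 8, which does not.
- A true 10 with one item ticked 1 instead of 2 gives 10 − 1 = 9, which falls below the cut.

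These show what is possible. They are not estimates of how often it occurs.

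**4. Timing of endpoint 6 and objective 5**

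Five of the six endpoints in Section 4.5 state 6 months; endpoint 6 does not. The only PHQ listed in the visible text is at about one month (Sections 5.1 and 5.2.4). Sections 5.3.1 and 5.3.2 place the second patient interview after the end of the intervention and at six months, which suggests a later time point for endpoint 6. Section 5, however, uses the term pre-intervention for the earlier comparator group, so endpoint 6 could simply mean the cohort that received the program. The text does not settle which. The enrollment and in-hospital list in Section 5.2.4 contains no depression measure, so only the post-discharge part of objective 5 has a listed measurement.

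**The case against.** The best defence is that the label may do little harm. The answers are printed in ascending order with their numbers, and that order signals the intended meaning. The community health worker (CHW) does the screening, and the form has a field for the initials of whoever completed it, so a staff member may well explain the options. In the visible text the cut of 10 has one use: purposive selection of up to 8 interviewees, who must also have been referred and who can qualify on the AUDIT-C instead. The pilot's main goal is feasibility and acceptability. All of this stands and limits the likely effect. It does not make the label right, and the form also tells the respondent to click an answer, so staff explanation cannot be assumed.

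On timing, the list in Section 5.2.4 is introduced as background and comorbidity measures. It has no six-month block at all, although six-month outcomes are described elsewhere in that section. Its silence is therefore weak evidence about what is planned. This also stands, and it makes the endpoint 6 and objective 5 points requests for clarification.

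A reader might go further in four ways that the documents do not support:

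- That the scale is reversed. The printed 2-point answer is open-ended, so it overlaps the 1-point answer and does not rank below it.
- That English scores are shown not to be comparable with the other forms. This is a risk only; no data on misreading or language use are given.
- That primary endpoint 7 (seeking services after screening and referral) is distorted. No PHQ-9 referral threshold is stated in the visible text.
- That endpoint 6 has no planned measurement. What is shown is that its date is missing.

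**Conclusion.** The English PHQ-9 is wrong as written on 9 of 9 scored items and should be corrected. Totals on that form may be misclassified around 10, in either direction, and one item is enough for someone at 9 or 10. Net direction, frequency and the share of participants given the English form are unknown. The conclusion about the label rests only on the conflict within the form, supported by the other two language versions. The consequences assume that at least some respondents take the wording literally.

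The missing date for endpoint 6 and the missing in-hospital measure for objective 5 are real but secondary, and the finding does not depend on them.

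**What to change.** **Main change.** On all nine items of Appendix 11, replace the 2-point label with the day-count wording of the form's own score row. Record form language and version for each completed PHQ-9, so that English forms filled in with the faulty label can be identified. Those forms cannot be rescored; flag them and report how many there are.

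**Clarifications.** State which time point defines secondary endpoint 6. If it is the one-month screen, make no claim about the effect of referral, because that screen comes before referral. Limit exploratory objective 5 to the period after discharge.

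**Cost.** These are text edits plus one recorded item per form, with no added participant contact. They are cheap but not free: Section 9.2 requires modifications to the protocol to be reviewed and approved, so they should go in as one minor modification. If the sponsor prefers to define endpoint 6 by a six-month PHQ-9, that lengthens the existing six-month contact and has to be done in three languages.

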8	Kuyenda kapena kukamba pang'ono-pang'ono kwambiri Kwamene mwina munaona? Kapena zosiyanako – kunkhala Kusankhazikika kapena kusapumula kuti munali kuyenda-yenda kwambiri kupambana nthawi zonse	 0.Kulibe ngankhale pang'ono  1.Masiku angapo  2.Kupambana pa hafu ya masiku  3.Pafupi-fupi masiku onse	

9	Maganizo yakuti chingankhale bwino kufa kapena Kuzichita mweka mu njira iliyonse	 0.Kulibe ngankhale pang'ono  1.Masiku angapo  2.Kupambana pa hafu ya masiku  3.Pafupi-fupi masiku onse
	Score "Masiku angapo".	
	Score "Kupambana hafu ya masiku":	
	Score "Pafupi-fupi masiku onse":	
	Enter Total Score:	
10	Ngati mwachonga mavuto yali yonse, kodi aya mavuto; Yachipanga bwanji kunkhala chovuta kwa inu kuchita nchito zanu; Kusamalira zinthu pa nyumba kapena kumverana ndi anthu ena? with other	 0.Sichokosa ngankhale pang'ono  1.Nichokosako  2.Ni chokosa kwambiri difficult  3.Nichokosa kwambiri
	Does the hard copy score match the database score?	 Yes  No
	If the scores do not match, please comment	<hr/> <hr/>
	Date form completed: (DD/MM/YYYY)	
	Form Completed by (initials):	

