9	Amatontonkanyo ayakuti kuti caba bwino nga mwalifwile nangu ukuicena mwebene munshila imbi	 0.Awe nelyo panono  1.Inshiku ishingiko  2.Ukucila pali hafu ya nshiku	

		 3.Mupepi na cila bushiku
	Score "Several days"	
	Score "More than half the days"	
	Score "Nearly every day"	
	Enter Total Score:	
10	Nga cakutila mwaconga amafya ayali yonse, bushe aya mafya yalengele ukuba icayafya kuli imwe ukucita imilimo, Ukusakamana ifintu pa ng'anda, nangu ukumfwana nabantu bambi	 0.Sichokosa ngankhale pang'ono  1.Nichokosako  2.Ni chokosa kwambiri difficult  3.Nichokosa kwambiri
	Does the hard copy score match the database score?	 Yes  No
	If the scores do not match, please comment	_____
	Date form completed: (DD/MM/YYYY)	
	Form Completed by (initials):	

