10	If you checked off any problems, how difficult has these problems made it for you to do your job, take care of things at home, or get along with other people?	 0. Not difficult at all  1. A bit difficult  2. Difficult  3. Very difficult
	Does the hard copy score match the database score?	 Yes  No
	If the scores do not match, please comment	<hr/> <hr/>
	Date form completed: (DD/MM/YYYY)	
	Form Completed by (initials):	

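### The English PHQ-9 has a wrong label on option 2 and an unclear item 9, Bemba item 10 carries Nyanja answer options, and no available text links a positive item 9 to action

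*Combined protocol and SAP*

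**What the plan says.** The community health worker (CHW) screens for depression about one month after discharge and refers where feasible (section 5.1; section 5.2.4 lists the PHQ among the one-month measures). The form exists in three languages: Nyanja (Appendix 9), Bemba (Appendix 10) and English (Appendix 11).

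The English form asks about the past two weeks. Under each of items 1 to 9, option 2 is "More than half a day". The score row for that option, lower on the same form, is "More than half the days". Item 9 is "The idea that it would be better to die or to do it yourself in any way".

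Item 10, on how difficult the problems made daily life, comes after the total-score row. In the Bemba form its option 2 is printed as "2.Ni chokosa kwambiri difficult", the same text as in the Nyanja form.

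On follow-up of a positive screen, the plan contains:
- referral to mental health services, reflected in primary endpoint 7 (section 4.4), section 5.3.2 and the six-month patient interview guide (Appendix 2);
- a PHQ-9 total of 10 or more, mentioned in section 5.3.2 for sampling referred patients for interviews;
- weekly meetings of CHWs with the community liaison officer (CLO), and an urgent call from the household to the CLO, who can bring in the physician. A raised pulse is the only example of a trigger (section 5.1);
- immediate escort to a facility for vital signs outside safe ranges (section 5.1);
- a study team member whom participants can reach by phone at any time (section 9.8).

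**The concern.** A patient who answers the English form sees a label that does not mean what the scoring key says. For item 9, the patient has to guess what the second half refers to. Bemba speakers are offered item 10 options in another language, two of which are nearly identical. The three forms may therefore not ask the same thing. Section 4.3 aims to describe depression prevalence, and section 4.5 lists depression level as a secondary endpoint.

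The second matter is participant safety. Item 9 is the one PHQ-9 item where a single positive answer may call for a same-day response, whatever the total. The alcohol form (Appendix 12) prints its own referral rule. The PHQ-9 forms print score rows, a total, a difficulty item and a data check, but no rule for action. The data check, "Does the hard copy score match the database score", compares two copies of the same score. It cannot detect a wrong label and does not prompt a response.

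**Working it through.** The plan states no figure on this point, so there is none to reproduce. The check compares the forms and does simple score arithmetic.

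1. **Option 2, English form.** Inputs: the two-week recall in the stem, the option label and the score row, all in Appendix 11. Two weeks = 14 days. The score row means more than 14 / 2 = 7 days, that is 8 to 14 days. The printed option, read literally, means more than 0.5 day. Option 1 refers to a few days; if that is taken as at least 2 (an assumption), the literal floor of option 2 (0.5) lies below that of option 1 (2), although option 2 carries the higher code. The label appears in 9 of 9 scored items, so a slip in reading the PDF is unlikely. The labels of options 1 and 3 also differ from their score rows, but only as near-synonyms.

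2. **Item 9, English form.** The item has two halves joined by *or*. The first asks about being better off dead. The second should add something, but it names no act: there is no word for hurt or harm, and what is to be done oneself is left open.

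3. **Item 1, English form.** It describes the problem as having a small amount of interest or pleasure. Taken literally, this affirms some interest and does not ask about a lack of it. This matters because the English form is the natural reference for checking the translations.

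4. **Item 10, Bemba and Nyanja forms.** Set side by side, the answer options are identical in 4 of 4 cases. In both forms, options 2 and 3 use the same words apart from a space and one stray English word. This can be seen without speaking either language. Item 10 is below the total-score row, so it does not enter the total.

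5. **Item 9 against the total-score cut-off.** Nine items scored 0 to 3 give a maximum of 9 × 3 = 27. Item 9 at its maximum with all others at 0 gives 3, which is below 10. With item 9 at 3, the other eight items must still add 10 − 3 = 7; with item 9 at 1, they must add 10 − 1 = 9. A cut-off on the total does not by itself pick up a positive item 9.

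6. **Routes to action.** None of the routes listed in the plan names item 9. Referral carries no urgency level. The weekly meeting may come days after the answer. The phone line depends on the participant calling.

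**The case against.** The strongest reply on the forms is that context rescues them. The two-week stem, the neighbouring options and the score row all steer a reader to the intended meaning of option 2, and item 9 can be understood as ending one's own life. The documents also contain no reference English text, so one cannot show from them what item 9 ought to say. Part of this stands. Only the lack of clarity is claimed, and the replacement wording below is a plain repair that the study team may replace with its authorised text. The conflict between option 2 and the score row needs no outside source.

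The strongest reply on safety is that the argument rests on absence. The list of triggers for the urgent call is open-ended, the tablet already prompts some actions and its logic is not shown, and consent and some other pages are not in the text available. This stands, and it limits that part to a request to name the trigger or point to it.

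Four stronger readings are tempting, and the documents do not support them:
- *The study has no procedure for suicide risk.* For the reasons just given, one can say only that no available text shows one.
- *Depression scores are distorted.* The ratio 7 / 0.5 = 14 between the two meanings of option 2 rests on a purely literal reading. Order and codes are kept, and no effect on scores is shown. The link from the one-month PHQ to the depression endpoint in section 4.5 is likely but not stated, and section 8.2.1 specifies no PHQ analysis.
- *Nyanja item 9 has the same fault as the English.* Its "Kuzichita mweka mu njira iliyonse" looks related to "mukuchita zinthu" in item 1, while Bemba item 9 has "ukuicena mwebene munshila imbi". Matching verb stems is not a verified translation, so this is only a reason to ask a speaker.
- *The trigger would cost only a few calls.* The documents give no rate of positive item 9 answers, and these patients are recently hospitalised and ill.

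**Conclusion.** The forms are wrong as written (high confidence): option 2 in 9 of 9 scored items on one of three language forms, an unclear item 9 on that form, and 4 of 4 answer options of Bemba item 10 in Nyanja, with options 2 and 3 almost indistinguishable in both translations. The size is limited: no shift in scores is shown, item 10 is outside the total, and no number of affected patients can be given because the documents report neither an item 9 rate nor a split by language. The sample size and the six-month comparison are untouched.

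Naming item 9 as a trigger is a cheap improvement (medium confidence). It assumes that neither the pages not available nor the tablet already does this. The arithmetic in its favour is that item 9 alone reaches at most 3 of the 10 points mentioned in section 5.3.2. Both changes should be made, since they correct an instrument that patients answer and cost little.

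**What to change.** **Forms.** In Appendix 11, change option 2 to "More than half the days" in all nine items. Reword item 9 to ask about thoughts of being better off dead or of hurting oneself, and reword item 1 so that it clearly asks about a lack of interest or pleasure. In Appendix 10, put the item 10 options into Bemba. In Appendices 9 and 10, make options 2 and 3 of item 10 distinct. Have speakers check both translations, item 9 in particular, against the corrected English. If screening has started, record the form version so that old and new answers are not mixed.

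**Section 5.1.** Add one line naming a positive item 9 answer (1 or more, or a threshold set by the study physicians), regardless of total score, as a trigger for the existing urgent call from CHW to CLO to physician. The physicians set the clinical response. If a procedure already covers this, one line pointing to it is enough. Section 5.2.4 does not say whether historical controls complete the PHQ. If they do, they have no CHW and need another route.

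**Cost.** Edits to the forms, a speaker check of two of them and one line in section 5.1. The downside is an unknown number of extra calls, some not urgent, handled by existing staff.
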